12.0 CRITERIA FOR THERAPEUTIC RESPONSE/OUTCOME ASSESSMENT

The same method of assessment (i.e. CT or MRI) and the same technique (i.e. with or without contrast) should be used to characterize each identified and reported lesion at baseline and every two cycles (+/- 1 week). A designated radiologist at MSKCC will interpret the study CTs or MRIs according to RECIST 1.1 criteria. The same radiologist/physician should perform the evaluation for the entire duration of the study.

Tumor response will be assessed using RECIST 1.1. Confirmation of response will not need to be required. A CT scan of the chest +/- abdomen/pelvis will be performed to demonstrate all known areas of measurable disease. The baseline study will occur no more than 4 weeks prior to first study drug administration. A CT scan with contrast will be the preferred method and modality of imaging. A CT scan without contrast or MRI can be used in patients with contraindications to radiographic contrast media used in CT scans. All patients must have at least one measurable disease lesion by CT or MRI.

All measurable lesions, up to a maximum of 5 lesions total, representative of all involved organs should be identified as target lesions and recorded and measured at baseline. Target lesions should be selected on the basis of their size, should be representative of all involved organs, and should lend themselves to reproducible repeat measurements. All other lesions (or sites of disease) should be identified as non-target lesions and should also be recorded at baseline. Definitions of response in target and non-target lesions are described in table 12.1. Table 12.2 provides overall responses for all possible combination of tumor responses in target and non-target lesions.

Table 12.1 Evaluations of Target Lesions	
Complete response (CR):	Disappearance of all target lesions
Partial Response (PR):	At least a 30% decrease in the sum of the diameters of the target lesions
Progressive Disease (PD):	At least a 20% increase in the sum of the diameters of the target lesions or the appearance of one or more new lesions
Stable Disease (SD):	Neither sufficient shrinkage to qualify for PR nor sufficient increase to qualify for PD

Table 12.2 Evaluations of Non-Target Lesions	
Complete response (CR):	Disappearance of all non-target lesions
Incomplete response/stable disease (SD):	Persistence of one or more non-target lesions
Progressive Disease (PD):	Appearance of one or more new lesions and/or unequivocal progression of existing non-target lesion

Table 12.3 Best Overall Response

Target Lesions	Non-Target Lesions	New Lesions	Overall Response
CR	CR	No	CR
CR	Incomplete/SD	No	PR
PR	Non-PD	No	PR
SD	Non-PD	No	SD
PD	Any	Yes or No	PD
Any	PD	Yes or No	PD
Any	Any	Yes	PD

Evaluation of Best Overall Response: The best overall response is the best response recorded from the start of treatment until disease progression, as defined in **Table 12.3**.

Evaluation of Toxicity: All patients who receive at least one dose of treatment with erlotinib and trametinib will be evaluable for toxicity.

Progression Free Survival (PFS): Duration of time from first treatment to time of progression or death, whichever occurs first.

Overall Survival (OS): Duration of time from first treatment to time of death.

13.0 CRITERIA FOR REMOVAL FROM STUDY

Patients may withdraw from the study at any time. Other reasons for study discontinuation include but are not limited to:

- Change in patient eligibility
- Non-compliance with the defined treatment plan
- Protocol violation
- Investigator's decision based on patient's best interest
- Withdrawal of consent
- Severe, unexpected toxicities/side effects
- Lost to follow up
- Death
- Progression of disease (defined by RECIST 1.1)

For the Phase 1 portion of the study, patients who withdraw from the study for reasons other than DLT without completing a full treatment cycle will be replaced.

14.0 BIOSTATISTICS

Phase 1: Safety Run In

Primary Objective: To determine the safety and tolerability of the combination of erlotinib 75mg by mouth once daily with trametinib 1.5mg by mouth once daily in patients with EGFR mutant lung cancer and acquired resistance to EGFR tyrosine kinase inhibitors.

Endpoints: Identify any dose limiting toxicities of the combination. A dose limiting toxicity is a binary

outcome where a patient either experiences a DLT or not. DLT is defined as any of the toxicities described in Section 9 that occurs within one cycle after initiation of treatment with erlotinib and trametinib.

Method: Up to six patients will be enrolled at dose level 0 (trametinib 1.5mg by mouth once daily and erlotinib 75mg by mouth once daily) and assessed for dose limiting toxicities (DLTs) for 1 full cycle (28 days). Toxicity will be graded according to NCI CTCAE version 4.0. If more than one patient develops a DLT, we will move on to the phase 2 portion of the study and the dose level -1 will be used. If ≤ 1 DLTs are detected, we will move on to the phase 2 portion of the study at dose level 0.

If 0-1 DLTs occur, and dose level 0 is used in the phase 2, the patients accrued during the phase 1 portion of the study will be followed for response assessment and included in the phase 2 portion of the study. Given an expected accrual rate of 2 patients per month, the accrual to the phase 1 portion of the study will be completed in about 3 months. Two to six patients will be enrolled in the phase 1 portion of the study.

Dose levels	Trametinib Dose	Erlotinib Dose
Dose Level 0	1.5mg PO qdaily	75mg PO qdaily
Dose Level -1	1 mg PO qdaily	100mg PO qdaily

Phase 2:

Primary Objective: To determine the ORR of the combination of erlotinib and trametinib in patients with EGFR mutant lung cancer and acquired resistance to EGFR tyrosine kinase inhibitors

Secondary Objective: To determine the progression free survival and overall survival and further assess the toxicity of trametinib and erlotinib

Methods: A Simon optimal two-stage trial design will be utilized to assess the primary endpoint of response rate (RECIST 1.1 CR+PR). This study will test the null hypothesis of 5% response rate against the alternative hypothesis of 25% response rate for patients with acquired resistance. A null hypothesis of 5% was chosen because all eligible patients have demonstrated progression and lack of response to erlotinib. The most effective treatment for both EGFR T790M positive and negative patients is afatinib and cetuximab which has a response rate of 29% but results in significant adverse events¹⁸. Subsequently, an alternative hypothesis of 25% was chosen for this study. The design chosen has a 10% type I error (falsely accepting a non-promising therapy), 10% type II error (falsely rejecting a promising therapy), for 90% power. In the first stage of this design, 9 patients will be treated. If 0 responses are seen in the first 9 patients, the trial will be stopped and declared negative. If at least 1 response is observed, than an additional 15 patients will be accrued to the second stage. At the end of the study, if 3 or more patients have a response out of a total of 24 patients enrolled, the combination of trametinib and erlotinib will be considered worthy of further investigation. Overall survival and time to progression will be estimated using the Kaplan-Meier method, with the follow-up starting at the initiation of therapy. Patients will be censored at the time of the last on-study evaluation if they do not experience the event of interest. Safety and tolerability will be summarized using descriptive statistics. The toxicities and the adverse events will be assessed for each patient according to the NCI CTCAE version 4.0 criteria. All correlative aims are exploratory and will be hypothesis-generating only.

Given an expected accrual rate of 2 patients per month, the accrual to the phase 2 portion of the study will be completed in about 6-12 months.

Correlatives: For the correlative studies, the analysis is primarily exploratory and hypothesis generating. Correlative studies will be performed on all patients participating in both the phase 1 and 2 portions of this clinical trial.

Method: EGFR T790M status will be determined for the biopsy samples obtained at the time of acquired resistance to EGFR TKI monotherapy. The portion of patients with T790M mutation will be calculated along with the exact 95% confidence interval. The expression of proteins such as BIM, TGFB2, vimentin, e-cadherin, n-cadherin, and neurofibromin will be quantified using immunohistochemical (IHC) staining in the biopsy tissue obtained and reported as a proportion of patients with each IHC score. Results will be summarized at each time point using descriptive statistics (mean +/- std). Graphical methods will be used to evaluate the way protein expression changes during the course of treatment.

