1.0 PROTOCOL SUMMARY AND/OR SCHEMA

Study Title:	A Phase 1/2 Trial of Trametinib and Erlotinib in Patients with EGFR-Mutant Lung Adenocarcinomas and Acquired Resistance to Erlotinib
Study Objectives:	
Phase 1: Safety Run In
 
Primary Objective: Determine the safety and tolerability of erlotinib 75mg by mouth once daily with trametinib 1.5mg by mouth once daily for patients with acquired resistance to erlotinib
 
Phase 2:
 
Primary Objective: Assess overall response rate (CR+PR) of trametinib when given in combination with erlotinib for patients with EGFR-mutant lung cancers and acquired resistance to erlotinib
 
Secondary Objectives: 1) Measure progression-free survival and overall survival among patients treated with trametinib and erlotinib 2) further define the toxicity profile of the combination
 
Correlative Studies:
 
Objectives: 1) Confirm BIM induction with MEK inhibition by assessing BIM protein expression by IHC on serial biopsies 2) Identify changes in protein expression related to apoptosis, EMT and NF1 expression 3) Perform transcriptome analysis (using RNA-seq) on tumor tissue from serial biopsies. 4) Perform next-generation sequencing based mutation testing to identify genetic alterations on tumor tissue from serial biopsies 5) Assess EGFR T790M status on all patients on study.

Patient Population:	Patients with locally advanced or metastatic lung adenocarcinomas with a confirmed EGFR mutation who have developed acquired resistance to EGFR tyrosine kinase inhibitor therapy
Number of patients:	
Phase 1: Maximum of 6 patients
 
Phase 2: Maximum of 24 patients (including up to 6 patients from Phase 1)

Inclusion Criteria:	
All patients must have:
 
 • Pathologic evidence of stage IV or recurrent lung adenocarcinoma that cannot be treated with curative intent • Somatic activating mutation in EGFR • Radiographic progression during treatment with erlotinib. Prior chemotherapy regimens are permitted. • Measurable (RECIST 1.1) indicator lesion not previously irradiated

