6.1 CRITERIA FOR SUBJECT ELIGIBILITY

6.2 Subject Inclusion Criteria

All patients must have:

- Pathologic evidence of advanced stage IV or recurrent lung adenocarcinoma reviewed at MSKCC
- Somatic activating mutation in EGFR Radiographic progression during treatment with erlotinib or any other EGFR TKI therapies.
- Any number of prior chemotherapy regimens is permitted.
- Measurable (RECIST 1.1) indicator lesion not previously irradiated
- KPS \geq 70%
- Age $>$ 18 years old
- Must have undergone biopsy after development of acquired resistance to erlotinib with available archived tissue (equivalent of \geq 10 unstained slides)
- Left ventricular Ejection Fraction \geq the lower limit of normal by ECHO or MUGA
- Adequate organ function:
 - - AST, ALT \leq 2.5 x ULN

- - Total bilirubin $\leq 1.5 \times \text{ULN}$
- - Albumin $\geq 2.6 \text{ g/dL}$ - Creatinine $< 1.5 \times \text{ULN}$ OR calculated creatinine clearance $\geq 50 \text{ mL/min}$
- - Absolute neutrophil count (ANC) $\geq 1,200 \text{ cells/mm}^3$
- - Hemoglobin $\geq 9.0 \text{ g/dL}$
- - Platelets $\geq 100,000/\text{mm}^3$

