8.1 PRETREATMENT EVALUATION

Study eligibility is based on meeting all of the study inclusion criteria and none of the exclusion criteria at screening and on Study Day 1 before study treatment administration. The following assessments will be conducted prior to subjects receiving their first dose of trametinib on this protocol. All aspects of the screening evaluation should be completed within 4 weeks of starting treatment:

- Documented presence of a somatic activating EGFR mutation
- Full medical history and physical examination
- Baseline tumor assessment of the CT scan of the chest (and other additional studies based on the patient's sites of disease). Tumor burden must be measurable using RECIST 1.1.
- Complete vital signs (pulse, blood pressure, temperature, respiratory rate) as well as weight and height
- 12 lead electrocardiogram (ECG) and echocardiogram within 1 month of study initiation
- Performance status
- Serum pregnancy test for women with child bearing potential
- Complete blood count with differential
- Comprehensive metabolic panel (glucose, blood urea nitrogen, creatinine, sodium, potassium, chloride, bicarbonate, calcium, total protein, albumin, serum bilirubin, alkaline phosphatase, ALT, AST)
- Ophthalmology Exam (See Section 10 for more details)
- Archival Tumor Tissue

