9.5 Correlative Studies: Biopsies will be required prior to start of study treatment and at the time of progression. At prespecified time points, and after additional informed consent, patients will

have image-guided core needle biopsies with 3-4 cores obtained. At least 2 cores will be immediately frozen in liquid nitrogen and sent to [name] lab.

The remaining cores will be fixed in formalin and sent to Surgical Pathology. Blood will also be used for IMPACT testing for next-generation sequencing based testing if not obtained previously.

DNA/RNA will be extracted from one flash-frozen core using an AllPrep® DNA/RNA mini kit (Qiagen). RNA quality will be assessed at the MSKCC integrative genomics (iGO) core facility using an Agilent Bioanalyzer 2100 platform. We will perform RNA-seq on all patients with sufficient tissue from the phase 2 cohort, to quantify changes in gene expression at various time points of treatment and to identify potential biomarkers of response to combination therapy. Extracted RNA (5ug) will be submitted to Genewiz for single-end 75bp reads on a HiSeq 2500 instrument. RNA samples that are limiting in quality/amount will be amplified using the Ovation® RNA-seq System V2 kit (NuGen) and submitted for RNA-seq as cDNA. We expect RNA yields from core biopsies to be limiting, thus we will not perform rRNA depletion prior to submission of samples. Analysis of RNA-seq data will be performed at the MSKCC Bioinformatics core facility. Remaining RNA will be frozen at -80C for validation of genes of interest highlighted by RNA-seq data. Validation will be performed using either RT-PCR or through the construction of a custom nanostring nCounter panel that includes genes of interest. One fixed core will be used for immunohistochemistry to determine protein expression for transcripts of interest, including: BIM, cleaved caspase 3, TGFB2, vimentin, e-cadherin, n-cadherin and neurofibromin. MSK-IMPACT, our next-generation sequencing based mutation platform that assesses for genetic alterations in 340 cancer-related genes will be used for molecular analysis.

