³CMP includes glucose, blood urea nitrogen, creatinine, sodium, potassium, chloride, bicarbonate, calcium, total protein, albumin, serum bilirubin, alkaline phosphatase, ALT, AST

⁴A single 12 lead ECG should be performed at screening and day 1 of every cycle +/- 2 weeks.

⁵Echocardiogram should be performed at screening and every three cycles +/- 2 weeks

⁶Response to therapy will be assessed by interval imaging studies every 2 cycles (8 weeks)+/- 2 weeks with response evaluated using RECIST version 1.1. Radiologic imaging will include a CT chest +/- abdomen/pelvis depending on sites of disease with or without contrast. If an appropriate imaging study is performed early for any reason (i.e. hospitalization), it can be used for disease assessment. CT scans should be completed if the patient comes off study for any reason other than progression. If a CT scan was completed within the last 8 weeks, it will not need to be repeated.

⁷ B-HCG testing (serum or urine) should be performed only in women of child bearing potential.

⁸ Tumor biopsy will be performed within 3 months of study initiation (unless archived tissue is available from a biopsy obtained after progression on erlotinib) and at time of progression +/- 4 weeks. Both patients on the phase 1 and phase 2 portion of the study will have biopsies performed.

⁹ IMPACT bloods will be drawn at screening for next-generation sequencing based testing.

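### Does the Section 6.2 wording on other EGFR TKIs undercut the reason given for the 5% null response rate?

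*Combined protocol and SAP*

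**What the plan says.** Section 14.0 (Phase 2 methods) sets a Simon optimal two-stage design with a 5% null, a 25% alternative and 10% for each error rate. The trial stops if none of the first 9 patients responds. Otherwise it continues to 24 and is positive with 3 or more responders. The null is explained in one sentence: "A null hypothesis of 5% was chosen because all eligible patients have demonstrated progression and lack of response to erlotinib".

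The passages that bear on who is eligible are these:

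- Section 6.2, progression criterion: "Radiographic progression during treatment with erlotinib or any other EGFR TKI therapies".
- Section 6.2, biopsy criterion: "Must have undergone biopsy after development of acquired resistance to erlotinib with available archived tissue".
- Section 8.1, on how the criteria combine: "Study eligibility is based on meeting all of the study inclusion criteria and none of the exclusion criteria at screening".
- Section 1.0, synopsis inclusion list: "Radiographic progression during treatment with erlotinib. Prior chemotherapy regimens are permitted".
- Table 10.1, note 8: "Tumor biopsy will be performed within 3 months of study initiation (unless archived tissue is available from a biopsy obtained after progression on erlotinib".
- Section 9.5, correlative studies: "Biopsies will be required prior to start of study treatment and at the time of progression".
- Section 14.0, correlative method: "EGFR T790M status will be determined for the biopsy samples obtained at the time of acquired resistance to EGFR TKI monotherapy".

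The Phase 2 objective in Section 2.1, the design statement in Section 4.2 and the recruitment screen in Section 7.1 all name erlotinib. The synopsis population row and the Section 14.0 objectives speak of EGFR TKIs as a class. Section 15.2 makes the eligibility section the test applied at registration.

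**The concern.** The trial has no control arm and the regimen contains erlotinib. The 5% null stands in for what would be uninteresting in the patients enrolled, and its only stated support is that they have all already failed erlotinib. The progression criterion, read alone, lets in a patient who failed gefitinib or afatinib and never progressed on erlotinib. The stated reason does not describe that patient, and Section 14.0 counts responses among all patients enrolled, with no analysis set that would leave the patient out.

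The decision rule rests on few events, so one responder from outside the described population could carry the trial past stage 1 or supply the third response at the end. If such patients had a higher background rate, the true type I error would exceed the planned 10%. The biopsy provisions in Table 10.1 note 8 and Section 9.5 make this look more plausible, because neither says that a fresh pre-treatment biopsy must follow erlotinib.

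**Working it through.** **1. Reproduce the design.** Inputs, all from Section 14.0: n1 = 9, stop at 0; 15 more patients; positive if total ≥ 3. Let X be the responders among the first 9 and Y those among the next 15, each with response probability p.

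P(positive) = P(X=1)·P(Y≥2) + P(X=2)·P(Y≥1) + P(X≥3)

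- At p = 0.05: 0.2985 × 0.1710 + 0.0629 × 0.5367 + 0.0084 = 0.0510 + 0.0337 + 0.0084 = **0.0931**.
- At p = 0.25: 0.2253 × 0.9198 + 0.3003 × 0.9866 + 0.3993 = 0.2072 + 0.2963 + 0.3993 = **0.9028**.

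A search over two-stage designs with error at most 10% and power at least 90% returns this same design as the optimal one. The figures are right for a 5% null.

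**2. Can a patient who progressed only on another TKI be enrolled?** Take a patient who progressed on gefitinib and never on erlotinib.

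- Progression criterion, Section 6.2: met.
- Biopsy criterion, Section 6.2: not met, since there was no resistance to erlotinib for a biopsy to follow.
- Section 8.1: every inclusion criterion must be met. The patient is not eligible.
- Section 15.2: registration confirms eligibility against this section, so the same answer applies there.

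The reference to other EGFR TKIs still has a use under this reading. It covers a patient resistant to erlotinib whose most recent progression came on a later EGFR TKI; Section 3.1 describes such agents in development for the resistant setting.

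**3. Do other passages reopen the question?**

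- Table 10.1 note 8 schedules a procedure. Its exception concerns tissue obtained after progression on erlotinib, so it presupposes a patient who had that progression. Its tension with Section 6.2 is about fresh versus archived tissue, which is a separate matter.
- Section 9.5 describes correlative sampling and admits nobody.
- The synopsis has no biopsy criterion, but its progression criterion names erlotinib outright.
- The class-wide phrases in Sections 1.0 and 14.0 are descriptive. Resistance to erlotinib is resistance to an EGFR TKI, so they do not contradict the narrower criterion.

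**4. What if some were enrolled anyway?** The documents give neither a share nor a background rate for these patients, so both are assumed here. Suppose their background rate is 10% and everyone else's is 5%.

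- 3 of 24: average rate (21 × 0.05 + 3 × 0.10)/24 = 0.05625; P(positive) ≈ **12.1%**.
- 6 of 24: average rate (18 × 0.05 + 6 × 0.10)/24 = 0.0625; P(positive) ≈ **15.2%**.
- If their rate is also 5%: 9.3%, unchanged.

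Using the average rate for everyone is an approximation; the exact value shifts a little with how many of these patients fall among the first 9. An error of 36.4% would need every patient in the trial to have a 10% background rate, which is not the situation in question.

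**The case for a change.** The strongest case for a change is that the cumulative reading is inferred and nowhere stated. No sentence says that a patient must have progressed on erlotinib whatever other TKI was used, and the word *or* in the progression criterion naturally reads as an alternative. Class-wide wording recurs, and Section 3.1 treats erlotinib, afatinib and gefitinib together, so a class-wide intent is conceivable. Busy staff could apply the progression criterion and treat the biopsy criterion as a tissue requirement only. The margin is also thin: the exact error passes 10% once the background rate exceeds about 5.16%.

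Part of this stands. The progression criterion in Section 6.2 is wider than its synopsis counterpart and wider than the sentence supporting the null, and the two Section 6.2 criteria would read better if they matched. The rest does not carry the point further. That the biopsy criterion also serves to secure tissue does not remove the condition it contains. The thin margin comes from a discrete design whose attained error lies just under its limit, and it would be the same with perfect eligibility wording. So would the dependence on single responders: at a true 5%, exactly three responders account for 0.0668/0.0931 = 71.7% of positive results, whoever those responders are. Finally, Section 3.1 gives these three drugs a common response rate and a common progression-free survival, which offers no ground for thinking that 5% is wrong after one of them and right after another.

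**Conclusion.** The mismatch is a drafting slip in one eligibility bullet, and the concern does not call for a change to the plan. Applied together, as Section 8.1 requires, the Section 6.2 criteria already exclude a patient who progressed only on another EGFR TKI, so the justification of the 5% null holds for everyone who can properly be enrolled. The stopping rule, success rule and sample size are correct, with exact error 9.3% and power 90.3%.

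The possible edits gain little. Writing the erlotinib requirement into the progression criterion restates what the biopsy criterion already imposes. Rewording the null's justification alters no result. Deliberately admitting the wider group is a choice about accrual, and splitting response by prior TKI within 24 patients would leave groups too small to interpret.

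This conclusion rests on the biopsy criterion being enforced at registration. The content of the eligibility checklist mentioned in Section 15.2 is not shown, so that cannot be confirmed from the documents. If enforcement lapsed for a few patients, the effect on type I error would range from none, at a 5% background rate, to about 12.1% or 15.2% with 3 or 6 such patients at an assumed 10%. Nothing in the documents points to such a rate.

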10.0 EVALUATION DURING TREATMENT/INTERVENTION

Tables 10.1 outlines the schedule of assessments applied to patients. If the subject is unable to have a study assessment taken within the defined time window due to an event outside of his or her control (e.g. clinic closure, personal emergency, inclement weather, vacation) the assessment should be performed as close as possible to the required schedule. More frequent assessments should be obtained if clinically indicated. Subjects will return to the study site within 30 days after their last dose of trametinib and erlotinib to complete end of study assessments outlined below. Additional follow up will occur for subjects with AEs related to study treatment that are ongoing at the time of this visit and for subjects with SAEs related to study treatment that occur after the time of this visit.

Table 10.1: Study Calendar								
1 cycle=28 days	Screening	Cycle 1				Cycle 2	Cycle 3+	At progression/off study
	Within 4 weeks unless otherwise noted	C1D1	C1D7	C1D8	C1D15	C2D1	C3+D1	
Informed Consent	X							
Medical History	X	X		X	X	X	X	X
Concurrent Medication Reconciliation	X	X		X	X	X	X	X
Physical Exam/Performance status ¹	X	X			X	X	X	X
Ophthalmology Exam ²	X					X		
Vital Signs and Weight ¹	X	X			X	X	X	X
Complete Blood Count w/ differential ¹	X	X			X	X	X	X
Comprehensive Metabolic Panel (CMP) ^{1,3}	X	X			X	X	X	X
12 lead EKG ⁴	X	X				X	X	
Echocardiogram ⁵	X						X ⁵	
Adverse Events Evaluation ¹	X	X		X	X	X	X	X
Radiologic Tumor Assessments ⁶	X						X	X
MRI brain/disease assessment	X							
B-HCG ⁷	X							
Tumor Tissue ⁸	X							X
IMPACT Bloods ⁹	x							

¹Study Assessments (physical exams, vitals, weight, CBC, CMP, adverse events evaluation) will be repeated C1D1, C1D8, C1D15 (first cycle), then monthly subsequently. C1 assessments have a window of +/- 3 days, C2 onward assessments have a window of +/- 2 weeks.

²Baseline Ophthalmic exam will include visual acuity, visual field examination, tonometry, slit lamp biomicroscopy of the anterior segment (with special attention to inflammation) and the posterior segment, and indirect fundoscopic examination with special attention to possible retinal abnormalities. Exams are required at screening, month 1 +/- 2 week, and month 6 +/- 4 weeks. Additional ophthalmic exams will be performed if symptomatically warranted.

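### Overall survival has no censoring rule of its own: Section 14.0 censors it at the last on-study evaluation, which other sections link to progression, and no survival follow-up is described

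*Combined protocol and SAP*

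**What the plan says.** Section 14.0 (Phase 2) sets the secondary objective: "To determine the progression free survival and overall survival and further assess the toxicity of trametinib and erlotinib". The analysis sentence reads "Overall survival and time to progression will be estimated using the Kaplan-Meier method", counted from the start of therapy. The next sentence is the only censoring rule in the supplied text, and it draws no distinction between the two endpoints: "Patients will be censored at the time of the last on-study evaluation if they do not experience the event of interest".

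Section 12.0 defines OS as the time from first treatment to death. It sets no on-study limit and no censoring date.

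The plan does not define on-study. Three places bear on it:

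- Section 13.0 lists "Progression of disease (defined by RECIST 1.1" among the reasons for discontinuing the study.
- The last column of Table 10.1 is headed "At progression/off study", and no follow-up column comes after it.
- Footnote 6 of that table says "CT scans should be completed if the patient comes off study for any reason other than progression".

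On the last visit, Section 10.0 says "Subjects will return to the study site within 30 days after their last dose of trametinib and erlotinib to complete end of study assessments".

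**The concern.** Kaplan-Meier estimates OS correctly only if a patient censored at a given time has the same future risk of death as those still under observation. A patient whose disease has just progressed generally does not. If leaving the study at progression fixes the OS censoring date, censoring is informative, and the curve does not in general estimate OS as Section 12.0 defines it.

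The rule applies to patients without the event, and the plan does not say whether deaths after leaving the study are collected. That leaves three possibilities:

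- **Deaths missed.** Deaths after the end-of-study window are not ascertained. The curve then rests on patients who are progression-free or only just progressed, and OS is mostly overstated.
- **Deaths counted, survivors censored early.** Later deaths enter as events at their true dates, while patients still alive are censored at the last on-study evaluation. Survivors are removed from the late risk sets, and OS is understated.
- **Everything dated.** All off-study deaths and contacts are collected and treated as evaluations. There is no bias.

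At stake is the credibility of a stated secondary result, which could be wrong in either direction.

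**Working it through.** **Step 1: follow-up after the last visit.** Deaths within 30 days of last treatment should be caught by the end-of-study visit (Section 10.0) and by SAE reporting (Sections 17.2 and 17.2.1). Beyond that, the supplied text describes:

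- follow-up of treatment-related AEs and SAEs (Section 10.0);
- reporting of later related events (Sections 17.2 and 17.2.1);
- follow-up of an already reported SAE that recurs or progresses, without time limit (Section 17.2.1);
- pregnancy follow-up (the Pregnancies text after Section 17.2.1).

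None of these is a vital-status schedule.

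**Step 2: the plan's own figures.** The plan gives no OS event count, power or follow-up time, so there is no OS figure to reproduce. The Simon design (0 of 9 stops; 3 or more of 24 succeeds; 5% against 25%) reproduces with type I error 0.093 and power 0.903. OS does not enter it.

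**Step 3: illustration.** The following rates are assumptions, not in the documents: exponential times, median PFS 4 months, median survival after progression 8 months, a fraction f = 0.10 of PFS events being deaths, and the last on-study evaluation 1 month after progression. Accrual is uniform over 12 months, from the plan's 2 patients per month: 24/2 = 12. Section 14.0 says "the accrual to the phase 2 portion of the study will be completed in about 6-12 months". At that rate, 6 months would yield only 12 patients. If 6 carry over from phase 1, the remaining 18 take 9 months.

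The hazards are λ = ln2/4 = 0.1733 and μ = ln2/8 = 0.0866 per month.

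*True OS.* S(t) = e^(−λt) + (1−f)·λ/(λ−μ)·(e^(−μt) − e^(−λt)). At 12 months this is 0.125 + 0.9 × 2 × (0.3536 − 0.125) = **0.54**.

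*Deaths missed.* After month 1, the ratio of just-progressed to progression-free patients at risk is R = (1−f)·λ/(λ−μ)·(e^(λ−μ) − 1) = 0.9 × 2 × 0.0905 = 0.163. The observed death hazard is (fλ + μR)/(1+R) = (0.0173 + 0.0141)/1.163 = 0.0270 per month. Month 1 contributes 0.0224 to the cumulative hazard, so the 12-month total is 0.0224 + 11 × 0.0270 = 0.320, and e^(−0.320) = **0.73**.

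*Deaths counted, survivors censored early.* This was simulated. With cut-off 6, 12 or 24 months after last accrual, 12-month OS is about **0.37, 0.44 and 0.51**. Censoring survivors at the cut-off while known alive returns 0.54 each time.

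**Step 4: sensitivity.** There were 36 scenarios: median PFS 2, 4 or 6 months; post-progression survival 6, 8 or 10 months; 5, 10, 15 or 20% of PFS events being deaths.

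| Case | Error in 12-month OS |
|---|---|
| Deaths missed | about 0 to +0.27; above 0.10 in 30 of 36 |
| Counted, cut-off 6 months | −0.32 to −0.08 |
| Counted, cut-off 12 months | −0.20 to −0.04 |
| Counted, cut-off 24 months | −0.07 to −0.01 |

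The counted rows use 12-month accrual. The zero arises where the hazard of death before and after progression is equal: 0.20 × ln2/2 = ln2/10 = 0.069. If the last visit falls anywhere within the 30 days, the deaths-missed error runs from −0.04 to +0.26, hence mostly overstated.

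**Step 5: sampling noise.** In simulated 24-patient trials of the central case (cut-off 12 months after last accrual), the mean (SD) of 12-month OS is 0.73 (0.15) with deaths missed, 0.54 (0.10) under an OS-specific rule, and 0.44 (0.12) with deaths counted and survivors censored early. Median OS is not reached in 75%, 2% and 0% of trials.

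**The case against.** The strongest reply is that the bias is conditional. The rule censors only patients who have not had the event, and Section 12.0 defines that event as death without an on-study limit, so a known later death counts on a plain reading. Section 11.3.7 has patients who stop trametinib for refractory hypertension continue follow-up, so stopping a drug and ending follow-up are not the same. Section 18.1 says the consent form describes likely follow-up, and those pages were not supplied. This stands.

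A reader might infer that later deaths will go uncollected, or that reported OS will certainly be too high. The documents support neither: they are silent on ascertainment, and the direction depends on it. A reader might also cite errors approaching 0.5. Those need either follow-up that stops at progression itself or a 6-month accrual that 2 patients per month does not support for 24 patients.

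The reply does not remove the gap. Counting later deaths while leaving survivors at their last on-study evaluation produces the understated curve. The general mentions of follow-up set no survival schedule. OS is also secondary, descriptive and untested, which limits the consequence but leaves it a stated objective.

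**Conclusion.** The point holds as a gap in a stated rule. OS shares its censoring date with time to progression, the plan's own structure links that date to progression, and nothing supplied gives OS a separate rule or a survival follow-up. Confidence is high on the wording. The bias is conditional on what on-study means and on whether later deaths are collected.

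In the central illustration the error is +0.19 (0.73 − 0.54) if later deaths are missed. If they are counted, it is about −0.17, −0.10 or −0.03 by cut-off, and the last is within sampling noise for 24 patients. Every survival rate behind these figures is assumed. The toxicity summary, like the response rule and sample size, is unaffected. This should be fixed, but it does not threaten the trial's main conclusion.

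**What to change.** - **Section 14.0:** give OS its own rule. The event is death from any cause, on or off study; otherwise censor at the date last known alive, with a stated data cut-off. Keep the last on-study tumor evaluation as the censoring date for PFS only.
- **Sections 10.0 (with Table 10.1) and 13.0:** state that leaving the study at progression does not end vital-status collection. It continues by chart review or telephone until death, withdrawal of consent or cut-off. Check that the consent wording covers this.
- **If that is not possible:** report the result as on-study survival and state the limitation.
- **Separately:** the same sentence in Section 14.0 analyses time to progression, while the Section 14.0 objective and the Section 12.0 definition are PFS, which counts death as an event. Replace the term with PFS.

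The cost is a short amendment and a small amount of vital-status checking for at most 30 patients (6 in phase 1 plus 24 in phase 2 if none carry over) at one institution. It adds no visits, procedures or patients.
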